### **Study Period:**

The study period begins at Visit 4 in which subjects will begin using Auto Mode. The subject will have follow up visits after Auto Mode has been turned on to adjust insulin pump settings and then continue wearing the study devices until the end of the study period.

### Manual Mode Settings

- High glucose alert limit recommend to be set at 300 mg/dL (16.7 mmol/L)
  - Alert Setting Options may be set per investigator discretion
- Low glucose alert limit recommend to be set at 70 mg/dL (3.9 mmol/L)
  - Subjects will be instructed to follow up with an SMBG confirmatory measurement when receiving a low alert
  - Alert Setting Options may be set per investigator discretion
- Predictive alerts and rate of change alerts are optional
- Consider setting the glucose target in the bolus wizard calculator to the same target as the Auto Mode (HCL algorithm), i.e. 120 mg/dL (6.7 mmol/L) or higher, based on investigator discretion.

### Settings for Auto Mode:

- Auto Mode (HCL) basal rate target for the closed loop algorithm is factory set at 120 mg/dL (6.7 mmol/L)
- Auto Mode correction target is factory set at 150 mg/dL (8.3 mmol/L)
- The Temp target setting in the pump may be used when subject exercises. Temp Target Threshold is set to 150 mg/dL (8.3 mmol/L)
- Alarms that are fixed into system:
  - When SG at or below 50 mg/dL (2.8 mmol/L)
  - When SG at or above 300 mg/dL (16.7 mmol/L) for one hour
  - When SG at or above 250 mg/dL (13.9 mmol/L) for 3 hours
- High glucose alert limit (i.e. the setting for a high glucose alert threshold based on sensor reading) is recommended to be set at 300 mg/dL (16.7 mmol/L)
  - Alert setting options may be set per investigator discretion
- Low glucose alert limit (i.e. the setting for a low glucose alert threshold based on sensor reading) is recommended to be set at 70 mg/dL (3.9 mmol/L)
- Alert setting options may be set per investigator discretion

- Subjects will be instructed to follow up with an SMBG confirmatory measurement when receiving a low alert
- Insulin carbohydrate ratios may be adjusted throughout study.
- Active insulin time may also be adjusted.

**Blood Glucose Monitoring Method:**

- Accu-Chek™\* Guide Link Study Meter

**SMBG recommendations:**

Subjects will be instructed to check their blood glucose at least 4-6 times per day and also before driving (as applicable) for diabetes self-management (SMBG), using the supplied Study Meter according to the user guide. Occasionally, subjects may receive a notification if the pump needs a blood glucose (BG) measurement to enter or to stay in Auto Mode.

## **5.1 Duration**

The study is anticipated to last no longer than 13 months from investigational center initiation to completion of all data entry and monitoring procedures. The study will target 5 months to complete subject enrollment. Subjects can expect to participate for approximately 2-3 months including the run-in and study periods.

## **5.2 Rationale**

Although the performance and safety of the MiniMed™ 670G System has already been studied in subjects in the United States, an evaluation involving Chinese subjects is required to support NMPA approval of the system.

## **6. Determination of Sample Size**

Based on US pivotal study outcome, the estimated difference of the TIR from run-in period to study period to be expected 5.3%. A sample size of 50 will achieve greater than 80% power to detect simple superiority using a one-sided t-test with a standard deviation of 13.0% at the significance level (alpha) of 0.025.

This study will enroll subjects between age of 14 and 75 years old, with an expected ratio (1:5) between Adolescents (14-17 years) and Adults ( $\geq 18$  years) to complete the study.

A total of up to 75 subjects will be enrolled at minimum 2 investigational centers and up to 6 investigational centers (hospitals) in China considering potential drop outs. A maximum of 30 subjects will be enrolled at each investigational center. Sites with less than 6 subjects will be pooled into 'pseudo-sites' of at least 10 subjects per pseudo-site. Pseudo-sites will be pooled by ranking those sites with less than 6 subjects by site number and pooling those sites in order of site number until the number of subjects reaches at least 10.

## **7. Statistical Methods**

---

### **7.1 Study Subjects**

#### **7.1.1 Disposition of Subjects**

The number of subjects enrolled in the study will be presented. The reasons for discontinuing prior to study completion will be summarized.

#### **7.1.2 Clinical Investigation Plan (CIP) Deviations**

All protocol deviations will be presented in the listings.

#### **7.1.3 Analysis Sets**

- Intention to Treat (ITT) Population  
The Intention to Treat (ITT) population will include all subjects who start the study period.
- Per Protocol (PP) Population  
The Per Protocol (PP) population will include all subjects who complete the study period and stay in Auto Mode  $\geq 80\%$  of study period and have no major deviations (e.g. protocol violation in eligibility).
- Efficacy Population  
The primary analysis will be performed on the ITT population. Sensitivity analysis will be performed on PP population.
- Safety Population  
The Safety Population will include all enrolled subjects.

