**SmartGuard™ features should not be activated**

#### Study Period Visits:

*Medtronic Confidential*

- Visit 4 (Office): 14 days after Visit 3 (+7 days)
  - Turn on Auto Mode
- Visit 5 (Office/ Telephone): 1 days after Visit 4 Office or telephone visit
  - Adjust settings as needed
- Visit 6 (Office/ Telephone): 2 days after Visit 4 Office or telephone visit
  - Adjust settings as needed
- Visit 7 (Office/ Telephone): 3 days after Visit 4 Office or telephone visit
  - Adjust settings as needed
- Visit 8 (Office/ Telephone): 4 days after Visit 4 Office or telephone visit
  - Adjust settings as needed
- Visit 9 (Office/ Telephone): 5 days after Visit 4 Office or telephone visit
  - Adjust Settings as needed
  - Provide training as needed
- Visit 10 (Office) – 14 days after Visit 4 (+3 days)
- Visit 11 (Office) – 20 days after Visit 4 ( $\pm 3$  days)
- Visit 12 (Office) – 30 days after Visit 4 ( $\pm 3$  days)
  - Remove Mobile App from Smartphone (if applicable)
  - Collect questionnaire(s)
  - Collect lab test for GA
  - End of Study

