## 14.5. Analysis Populations and Handling of Missing Data, Error

Data entry error or non-reasonable values will be resolved before data analysis. No imputations will be done for missing data.

The primary study population is the Intention to Treat (ITT) population, which consists of subjects who entering study period.

The Per Protocol (PP) population is defined as subjects who stay in Auto Mode  $\geq 80\%$  of Study Period and have no major deviations.

The safety population consists of all enrolled subjects.

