## **5. Investigation Plan**

This study is a multi-center, single arm study in insulin-requiring subjects with type 1 diabetes who are 14 years of age and older. The run-in period will be approximately up to 35 days long, followed by a study period that will be approximately up to 33 days in duration.

The study is anticipated to last no longer than 13 months from investigational center initiation to completion of all data entry and monitoring procedures. The study will target approximately 5 months to complete subject enrollment. Subjects can expect to participate for approximately 2-3 months including the run-in and study periods.

A total of up to 75 subjects (aged 14-75) will be enrolled at a minimum 2 investigational centers and up to 6 investigational centers (hospitals) in China to have at least 50 subjects who complete the study.

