### 7.9.2 Secondary Endpoints

- Time in hypoglycemic range (% of SG): SG < 70 mg/dL (3.9 mmol/L), 60 mg/dL (3.3 mmol/L) and 54 mg/dL (3.0 mmol/L)
- Time in hyperglycemic range: SG > 180 mg/dL (10 mmol/L), 250 mg/dL (13.9 mmol/L) and 350 mg/dL (19.4 mmol/L)
- Glucose variation: the standard deviation (SD) of SG and the glucose coefficient of variation (CV)
- Change of Total Daily Dose (TDD) of insulin and weight from baseline to EOS

- Time spent in Auto Mode (HCL) versus time spent in Manual Mode (open loop)
- Stratified by HbA1c Ranges (< 7%, 7 – 7.5%, 7.5 – 8%, > 8%)
  - Time in target range (% of SG): 70 mg/dL (3.9 mmol/L) ≤ SG ≤ 180 mg/dL (10 mmol/L)
  - Time in hypoglycemic range (% of SG): SG < 70 mg/dL (3.9 mmol/L), 60 mg/dL (3.3 mmol/L) and 54 mg/dL (3.0 mmol/L)
  - Time in hyperglycemic range: SG > 180 mg/dL (10 mmol/L), 250 mg/dL (13.9 mmol/L) and 350 mg/dL (19.4 mmol/L)

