## 7.12 Changes to Planned Analysis

Not Applicable.

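### Does the per-protocol rule of 80% time in Auto Mode need a stated denominator, and must SAP 7.12 record the added completion condition?

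*SAP*

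**What the plan says.** SAP 7.1.3 sets the PP population as follows: "The Per Protocol (PP) population will include all subjects who complete the study period and stay in Auto Mode" for at least 80% of the study period, without major deviations. The same section makes ITT the primary analysis set and gives PP a supporting role: "Sensitivity analysis will be performed on PP population".

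Protocol 14.5 has the same threshold and the same deviation condition but does not ask for completion: "The Per Protocol (PP) population is defined as subjects who stay in Auto Mode" for at least 80% of the study period. SAP 7.12, the place for changes to the planned analysis, is marked not applicable.

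On the length of the period, SAP 5 says "The study period begins at Visit 4 in which subjects will begin using Auto Mode". Protocol 9.1 places the last visit at "Visit 12 (Office) – 30 days after Visit 4", with a window of 3 days either side, and marks it as the end of the study. The overview in SAP 5 describes a run-in "followed by a study period that will be approximately up to 33 days in duration". SAP 7.4 says that device data are not imputed.

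**The concern.** A percentage needs a denominator, and neither document writes one out in operational terms. Three candidates could be put forward: the subject's own time from Visit 4 to Visit 12, the scheduled 30 days, or the 33-day figure in the design overview. They can sort the same subject differently. With 23 Auto Mode days and Visit 12 on day 27, the share is 85.2%, 76.7% or 69.7%, so the subject enters PP under the first reading only.

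The trial is single-arm and PP is the only sensitivity analysis named. Membership depends on Auto Mode data, so a rule left open could in principle be settled after those data and the glucose results are known. SAP 7.2 sends departures from the plan to the Clinical Study Report, which does not fix membership beforehand.

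The completion condition adds to the unease. It narrows the protocol's definition, and the section meant for such changes does not record it.

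**Working it through.** **The plan's own figure.** Protocol 14.4 and SAP 6 claim more than 80% power with 50 subjects, a mean change of 5.3 points, SD 13.0 and one-sided alpha 0.025. For a paired t-test the noncentrality is 5.3/13.0 × √50 = 2.88 on 49 degrees of freedom, and power is 80.7%. The claim reproduces. The primary analysis is on ITT, so nothing in the PP definition alters this figure.

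**Which denominator the text supports.** Visit 12 falls on day d, from 27 to 33. The share of own time needed to enter PP under a fixed divisor D is 0.80 × D/d.

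| Denominator | Visit 12 on day 27 | day 30 | day 33 |
|---|---|---|---|
| Own time | 80% (21.6 days) | 80% (24.0 days) | 80% (26.4 days) |
| Fixed 30 days | 88.9% | 80.0% | 72.7% |
| Fixed 33 days | 97.8% | 88.0% | 80.0% |

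Three things point to own time.

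1. Both documents name the base as the study period and give its start (Visit 4) and its end (Visit 12).
2. The 33 days is an upper limit, 30 + 3, not a length. As a divisor it would ask near-continuous Auto Mode use of someone who attended at the early edge of the window. A fixed 30 days gives a day-33 completer in Auto Mode throughout 33/30 = 110%.
3. The completion condition does real work only under own time. A subject who leaves on day 15 with 13 Auto Mode days has 13/15 = 86.7% of own time and would enter PP without it. Against 30 days the share is 13/30 = 43.3%, and the subject is out anyway. With a 30-day divisor, completion changes the result only for exits on days 24 to 26 at 100% use, or on day 26 at 95% use. With 33 days it never does, since 26/33 = 78.8%.

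**If someone used 30 days all the same.** The documents give no Auto Mode usage figures, so these inputs are assumptions: 50 completers, mean use 80% to 90%, SD 8 to 12 points (beta distribution), Visit 12 spread evenly over days 27–33 or 29–31. Between own time and 30 days, 1.1 to 10.3 subjects change status. The changes run both ways and largely cancel: net PP size moves by 0.1 to 2.7 subjects. At the planned effect and SD, power on the PP set moves by less than 4 points.

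**Time without device data.** This is the part that stays open. In a 30-day period, 80% of elapsed time is 24.0 Auto Mode days. If only time with data counts, the requirement is 0.80 × coverage × 30.

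| Assumed data coverage | Auto Mode days needed | Share of elapsed time |
|---|---|---|
| 100% | 24.0 | 80% |
| 95% | 22.8 | 76% |
| 90% | 21.6 | 72% |
| 80% | 19.2 | 64% |

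A subject with 23 Auto Mode days in 30 is out on elapsed time (76.7%) and in if 27 days carry data (23/27 = 85.2%).

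**The case for a change.** The best case for a change is that it costs two or three lines in the SAP, needs no protocol amendment, and closes a choice that could otherwise be made with results in hand. Data gaps strengthen it. At an assumed 90% coverage the effective threshold falls from 80% to 72% of elapsed time, and no sentence in either document excludes that reading. The completion condition is a real difference from Protocol 14.5, and no other section of the SAP records it.

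All of that is accurate, and the gap and the missing entry both stand. The consequence is what falls short. Writing down own time would record the reading an analyst would take without being told. An entry in SAP 7.12 would alter no result, because SAP 7.1.3 already states the condition openly. The treatment of gaps can move borderline subjects, but only in and out of a supporting analysis with no pass/fail role.

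A further argument is that PP contains no early withdrawals, so agreement between ITT and PP says nothing about dropout. That is correct, but the plan never claims that it does.

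**Conclusion.** No change follows. The denominator is named, and its natural meaning is each completer's own time from Visit 4 to Visit 12. The fixed 30-day and 33-day divisors, which produce most of the apparent disagreement, fit the text poorly. Two loose ends are real: the unstated handling of time without device data, which is a detail that analysts settle in programming and can state beside the PP table, and the unrecorded completion condition, which is a clerical omission.

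Both are confined to the PP sensitivity analysis. The ITT test, the pass/fail criterion and the 80.7% power at 50 subjects are the same under every reading. The judgement that own time is the natural base rests on the wording and visit schedule alone. The counts of subjects who change status, and the effect of data gaps, rest on assumed Auto Mode use, visit timing and data coverage, none of which the documents supply.

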### 8.2. Subject Enrollment

Subjects will be considered enrolled in the study upon signing the Informed Consent Form (ICF) and

*Medtronic Confidential*

assent form (if applicable).

A subject will be assigned a unique study subject identification (ID) via the eCRF, which is a 9-digit code (329XXXXXX). The first three numbers refer to the CIP number (329), the next three numbers refer to the investigational center number, and the last 3 numbers refer to the subject number assigned during Visit 1 (e.g., 329002001 is subject 001 from site 002).

The investigator will maintain a log of all subjects enrolled in the clinical study, assigning a subject ID linked to their names, alternative subject ID, and contact information.

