## 9. Study Procedures

### 9.1. Study Timeline

#### Visit Schedule:

#### **Run-in Period Visits: To be completed approximately up to 35 days**

[figure not shown]
- Visit 1: Screening (Office):
  - Consent
  - Collect demographic and baseline characteristics:
    - Age
    - Gender
    - Race
    - Ethnicity
    - Height and Weight
  - Obtain prior Medical History
  - Collect concomitant medications
  - Labs (pregnancy test [if applicable], HbA1c, TSH, Hct, GA and eGFR)
  - Screening Requirements
- Visit 2: Run-in Period Start - Visit 2 (Office): 2 - 7 days after Visit 1
  - ***Eligibility has been confirmed including labs***
  - **All eligible subjects:**
    - Start study pump; provide pump training
    - Collect questionnaire(s)
    - Collect information about food consumed in last 24 hours (food log)
  - Subjects who are using pump **with** CGM at Screening:
    - Visits 2 and 3 may be combined
    - Start CGM, provide CGM training
    - Start CGM run-in (2 weeks)
    - Install Mobile App to Smartphone (if applicable)
    - System is set Manual Mode (Sensor Augmented Pump only):  

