**SmartGuard™ features should not be activated**
- Visit 3: Start CGM 0-7 days after Visit 2
  - Subjects who are using pump **without** CGM at Screening:
    - Start CGM, provide CGM Training
      - Recommend that this visit take place 5-7 days after Visit 2
      - Start CGM run-in (2 weeks)
      - Install Mobile App to Smartphone (if applicable)
      - System is set Manual Mode (Sensor Augmented Pump only):  

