### **Overview of the Run-in and Study Periods:**

#### **Run-in Period:**

After enrollment and passing Screening requirements, subjects will be trained on pump use as well as the use of Continuous Glucose Monitoring (CGM) with transmitters and sensors.

The run-in period will be used to allow subjects to become familiar with new study devices. During the run-in period study subjects will be using the Study Pump (MiniMed™ 670G) and CGM with only the Sensor Augmented Pump (SAP) function activated (i.e. SmartGuard™ features such as Suspend on Low and Suspend before Low will remain turned OFF).

All subjects will be trained on the study devices and diabetes management principles, such as the treatment of hyperglycemia and hypoglycemia. A training checklist consisting of review of the MiniMed™ 670G system features will be completed and collected for each subject to ensure competency. In addition, there will be training regarding access to oral glucose, oral carbohydrates or glucagon in case of hypoglycemia.

For study purposes, subjects will be instructed to perform SMBG if they are experiencing a severe hypoglycemic event, severe hyperglycemic event or Diabetic Ketoacidosis (DKA). As a precaution, subjects will be told that they should keep their own insulin pump supplies in a safe place and to have back up supplies on hand (such as insulin and syringe) in the event they are asked to revert back to their own therapy during the study or experience study pump issues (i.e. infusion set occlusion with high glucose).

Subjects will be instructed to insert glucose sensors only in the locations that are specified in the User Guide materials. Reminders will be given to subjects at each office visit. Information about sensor insertions will be collected on an electronic Case Report Form (eCRF) in the study database, i.e. insertion location.

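### The only safety set is everyone who signed consent, so device-related percentages may be diluted by subjects who never start a device, and run-in events are not separated from study-period events

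*SAP*

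**What the plan says.** SAP 7.1.3 defines one safety set: "The Safety Population will include all enrolled subjects". Protocol 14.5 agrees: "The safety population consists of all enrolled subjects". Protocol 8.2 fixes when enrolment happens: "Subjects will be considered enrolled in the study upon signing the Informed Consent Form (ICF".

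Device use comes later. SAP section 5 gives the order: "After enrollment and passing Screening requirements, subjects will be trained on pump use". Protocol 9.1 times the next step as "Visit 2: Run-in Period Start - Visit 2 (Office): 2 - 7 days after Visit 1". Eligibility, including laboratory results, is confirmed at that visit, and the entry for eligible subjects reads "Start study pump; provide pump training".

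The run-in uses the study pump and CGM with the SmartGuard features off. The study period, with Auto Mode, begins at Visit 4 (SAP section 5).

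SAP 7.9.3 and 7.10 repeat one list: SAE, SADE, UADE, and the incidence of severe hypoglycemia, severe hyperglycemia and DKA. The events are collected in a single window from consent to study end. Neither section names a denominator, a split by period or patient-days. SAP 7.7 (Treatment Characteristics) is marked not applicable. SAP 7.1.1 promises the number enrolled and the reasons for discontinuation, but not the number who started the pump. The ITT set, subjects who start the study period, is assigned to the efficacy analysis only.

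**The concern.** Safety is the first-named part of the primary objective, and this is a single-arm registration study. With no control group, the absolute incidence is the safety evidence, so its denominator should describe people who used the device. A subject who fails screening cannot have a device-related event. Counting that subject can only lower a device-related percentage.

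The second issue does not depend on screen failures. A single tabulation from consent to study end does not show whether an event arose in run-in, with the SmartGuard features off, or after Visit 4. A reader who wants to know what happened once Auto Mode was introduced would not find it in the planned summary.

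**Working it through.** The documents give no safety percentage to reproduce. Their stated durations can be checked against the visit windows, and they agree.

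**Inputs**
- Enrolled: up to 75; at least 50 completers (SAP section 5).
- Visit 1 to Visit 2: 2 to 7 days (protocol 9.1).
- Visit 2 to Visit 3: 0 to 7 days (protocol 9.1, "Visit 3: Start CGM 0-7 days after Visit 2").
- Visit 3 to Visit 4: 14 to 21 days (protocol 9.1).
- Visit 4 to Visit 12: 30 ± 3 days, that is 27 to 33 (protocol 9.1).
- Number who consent but never start the pump, S: not given. Assumed to be 0, 5, 10 or 15.

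**Check of the stated durations.** Visit 1 to Visit 4 is at most 7 + 7 + 21 = 35 days, and the study period is at most 33 days. Both match the stated maxima.

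**Device-related percentages.** Let x subjects have a device-related event. The all-enrolled figure is x/75 and the device-exposed figure is x/(75 − S). Their ratio is (75 − S)/75 = 1 − S/75, so the relative understatement is S/75:
- S = 0: 0/75 = 0%
- S = 5: 5/75 = 6.7%
- S = 10: 10/75 = 13.3%
- S = 15: 15/75 = 20.0%

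With 75 enrolled and 50 completers, S cannot exceed 25. The extreme bound is therefore 25/75 = 33.3%, and only if every non-completer left before Visit 2. In absolute terms, three subjects with an event and S = 15 would read 3/75 = 4.0% instead of 3/60 = 5.0%.

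**No events.** The percentage is 0% on either set. Only an upper limit would differ: the exact two-sided 95% limit, 1 − 0.025^(1/n), is 4.8% for n = 75 and 6.0% for n = 60. The SAP does not plan such a limit.

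**All-cause events.** These can move the other way. Suppose 2 of 70 starters have an event, and 1 of 5 non-starters has one between consent and Visit 2. The all-enrolled figure is (2 + 1)/75 = 4.0%, against 2/70 = 2.9% of starters.

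**Period.** Device days before Visit 4 are (0 to 7) + (14 to 21) = 14 to 28, and after Visit 4 they are 27 to 33. The run-in share of a completer's device days runs from 14/(14 + 33) = 29.8% to 28/(28 + 27) = 50.9%.

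To show what the single tabulation hides, assume 75 enrolled, 65 pump starters and 60 who enter the study period, with three subjects who each have one event:
- 2 in run-in and 1 in the study period: 3/75 = 4.0% overall; by period 2/65 = 3.1% and 1/60 = 1.7%.
- 0 in run-in and 3 in the study period: 3/75 = 4.0% overall; by period 0/65 = 0% and 3/60 = 5.0%.

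The overall figure is the same in both cases.

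**The case against.** The strongest reply is that the plan never says safety percentages will be taken on all enrolled subjects. SAP 7.9.3 and 7.10 list events and name no denominator. This stands. A reader might infer that the reported percentages are diluted as a matter of fact, but the documents do not support that. Dilution follows only if the sole safety set is used as the denominator and at least one consented subject does not start the pump.

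A reader might also try to project a size from the US pivotal trial's 28 device-related events in 12,389 patient-days. That figure counts events, not subjects. It does not give the number of device starters here who will have one.

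It is also fair that the all-enrolled set matches the collection rule, which starts at consent, and that the SAP and protocol agree with each other. The set is a sound basis for listings and captures events before Visit 2, including those from screening procedures. What is missing is an additional set.

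Finally, much of the information could be recovered. Event start and end dates and causality are recorded (protocol 11.1), and the Clinical Events Committee may review the critical events and assesses device relatedness (protocol 12.1). That limits the harm. It does not replace a prespecified tabulation, and the planned disposition summary does not promise the count of pump starters needed to rebuild the denominator.

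**Conclusion.** The point holds as a gap in the safety analysis that should be fixed. Its denominator part is conditional: device-related percentages are understated by S/75, or 0% to 20.0% relative for 0 to 15 assumed non-starters among 75, and the true S is unknown. The direction for all-cause events is not fixed. The period part is unconditional: the plan has no split, and run-in makes up about 30% to 51% of a completer's device days.

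Three stronger readings are not supported:
- That the trial's success or stopping is at risk. The primary test, the pass/fail criterion and the stopping rules do not use this set.
- That run-in dropouts should be excluded. Those who started the pump were exposed and belong in the denominator.
- That a period split separates Manual Mode from Auto Mode. Some study-period time is also in Manual Mode: SAP 7.9.2 makes the comparison of time in each mode a secondary endpoint, and protocol Table 3 lists situations in which switching Auto Mode off is recommended.

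**What to change.** Make the change in the SAP.
- In 7.1.3, keep the all-enrolled set for listing adverse events from consent.
- Add a device-exposed safety set: subjects who start the study pump at Visit 2. Take pump start from the visit record or the pump upload. The disbursement date alone is not enough, because disbursement is not pump start.
- Use the new set as the denominator for device-related events, and for severe hypoglycemia, severe hyperglycemia and DKA with onset after pump start.
- In 7.9.3 and 7.10, tabulate these by period of onset: run-in (Visit 2 to Visit 4) on the device-exposed set, and study period (Visit 4 to exit) on subjects who start it.
- Give denominators and patient-days, since the periods differ in length. Label the columns run-in and study period, not by mode.
- State in advance how an event dated on the day of Visit 4 is assigned.

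Protocol 14.5 can be aligned at the next amendment. A separate one is not needed for this: protocol 16.8 sends even administrative amendments to the ethics committee, and the SAP already refines a protocol set on its own by adding study-period completion to the per-protocol definition.

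The cost is SAP wording and one or two extra columns per safety table. No new data are needed. Reported incidences may be slightly less favourable.
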